103 operative treatment of LHCF based on MRI performed without sedation or anesthesia and seeks to
104 dramatically lower the need for surgery. Objectives are to describe functional outcome, radiological
105 healing, secondary fracture displacement and any complications after two years. The investigators
106 hypothesize that undisplaced and minimally displaced LHCF can be treated non-operatively based on
107 MRI findings with good functional outcomes after two years. A cohort study design is used to follow 50
108 children with LHCF.

109 3 General information/responsibilities

110 The International Conference on Harmonization for Good Clinical Practice (ICH-GCP) and ISO 14155
111 guidelines define the responsibilities of the sponsor and investigators in the context of the study.
112 Specific topics, such as the permission from the responsible EC, are defined separately in the CIP. The
113 study site undertakes to guarantee correct and prompt implementation, documentation, and
114 transmission of the study data.

115
116 In the context of the study, the participating study site will return the completely documented cases.
117 Completely documented means that all FU visits have been carried out for the cases included in the
118 study and that these assessments are recorded on the electronic Case Report Forms (eCRFs) specially
119 designed for this study. Furthermore, the necessary radiological investigations must be performed at the
120 FU visits.

121 3.1 Responsibilities

Principal Coordinating Investigator
[name]
MD

Department of Orthopedic Surgery Copenhagen
University Hospital - Herlev
and Gentofte, Copenhagen, Denmark

[contact]
[contact]
E-Mail [contact]

Sponsor
Copenhagen University Hospital
Herlev and Gentofte

Department of Orthopedic Surgery and
Department of Radiology and Scanning
Copenhagen University Hospital
Herlev and Gentofte
Copenhagen, Denmark

122
123
124
125
126

127 4 Background and literature review

128 4.1 Definition and epidemiology

129

130 Fractures of the distal humerus account for 5-10% of all pediatric fractures but constitute up to 30% in
131 children aged 4-9 years of age [6–10]. Fractures of the lateral humeral condyle account for 10-20% of
132 all elbow fractures in children making it the second most frequent after supracondylar fractures
133 [3,11,12].

134

135 LHCF are usually the result of a fall on an outstretched arm with either the extensor-supinator mass

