 291 system. Parents are usually very keen to take their children for follow-up appointments making the risk
 292 of missing an appointment low. Any participants who miss an appointment will be contacted by phone to
 293 reschedule.

294

295 Table 1: Study schedule

296

Assessment parameters	Out-patient clinic visits and imaging procedures *										
	Visit 1**	Visit 2	Visit 3	Visit 4	Visit 5	Visit 6	Visit 7	Visit 8	Visit 9	Visit 10	
	Injury (day 0)	Screening	Information visit	Enrollment and consent	5 (± 3) days	12 (± 3) days	4 weeks	3 months	6 months	12 months	24 months
Eligibility	X										
Patient information		X									
Consent			X								
Demographics			X								
MRI				X							
If applicable - Control-MRI					(X)						
Cast removal***						X					
Radiographs and clinical exam					X	X	X	X	X	X	

297

298 * All FU visits with the defined time windows are calculated from the day of injury (i.e. day 0).

299 ** Telephone interview.

300 *** Casting may be prolonged two weeks in case of lack of callus formation at four weeks.

301

302 6.2.1 Visit 1: Screening (by phone)

- 303 • As described in section 6.1.4, the parents of potential study patients are informed about the study
304 over telephone by the PI.

305 6.2.2 Visit 2: Information visit

- 306 • All inclusion and exclusion criteria are checked to decide if the patient can participate in the study.
307 • Specific procedures for enrollment of pediatric patients are undertaken. A more detailed description
308 of the enrolment of participants and informed consent process is provided in section 6.1.4 and 10.
309 • Before any study-specific examinations are performed, the patient's parents give written informed
310 consent to participate in the study according to the CIP.

311 6.2.3 Visit 3: Enrolment, consent and preparation for MRI

- 312 • Obtain baseline demographics
313 • Book MRI
314 • Prepare child for MRI using the Child Centered Care model described in section 6.3
315 • Data verification and entry into the eCRF

316 6.2.4 Visit 4: MRI (5 (± 3) days)

- 317 • The MRI is performed according to the Child Centered Care model described in section 6.3
318 • Results of the MRI are given to the parents by phone
319 • Any necessary adjustments to the treatment plan is made
320 • Entry into the eCRF

321 6.2.5 ONLY if applicable: Control-MRI (12 (± 3) days)

- 322 • If an unstable Song stage 3 fracture is diagnosed based on the initial MRI an additional control MRI

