323 is performed during this visit
324 • Results of the MRI are given to the parents by phone
325 • Any necessary adjustments to the treatment plan is made
326 • Entry into the eCRF

327 6.2.6 Visit 5: Radiographs and clinical examination (12 (± 3) days)

- 328 • Plain radiographs of injured elbow without cast (AP, ML and IO)
329 • Clinical examination
330 – Cast condition
331 – Assessment of pain and use of pain medication
332 – Neurovascular status of the hand
333 • Entry into the eCRF

**334 6.2.7 Visit 6, 7, 8, 9 and 10: Radiographs and clinical examination (4 weeks and 3, 6, 12 and 24
335 months).**

- 336 • Plain radiographs of injured elbow without cast (AP, ML and IO)
337 • Clinical examination
338 – Assessment of pain and use of pain medication
339 – Neurovascular status of the hand
340 – Bilateral elbow assessment according to Mayo Elbow Performance Score (MEPS)
341 – Bilateral carrying angle of the elbow measured in degrees by goniometer
342 • Entry into the eCRF

343 **6.2.8 Unscheduled visits**

344 Unscheduled visits can take place at any time during the study if a need occurs or if the investigator
345 considers this to be appropriate for patient care. Information collected between study visits are to be
346 documented at the next regular study visit with the following exceptions:

- 347 • If a patient drops out of the study, a dropout form is completed at the time of dropout

348 **6.2.9 Premature study termination**

349 Patient participation in the study may end prematurely for one of the following reasons:

- 350 • Patient withdrew informed consent
- 351 • Protocol violation
- 352 • Investigator's discretion (e.g. patient noncompliance with CIP)
- 353 • Unknown/lost to FU

354

355 For each case of premature termination detailed information will be obtained explaining the
356 circumstances leading to the termination. This will be recorded on a dropout form in the eCRF.

357

358 If patients are withdrawn from the study, any collected data will be censored. Censoring allows this
359 collection of data to be accounted for in the analysis.

360 **6.3 Study treatments**

361

362 This study is not investigating any medical device. All devices in this study will be used per standard of
363 care at the participating institutions.

364 **6.3.1 Emergency treatment**

365 All patients who sustain a LHCF are initially treated in the ED with an above elbow splint. Parents and,

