456 **Figure 5 - Modified Mayo Elbow Performance Score.**
 457

458

459 **7.2 Secondary outcomes**

460 **7.2.1 MRI results**

- 461 • Proportion of successful MRIs defined as a completed scan with an image quality that is useful for
- 462 analysis by the radiologist.
- 463 • MRI findings.
- 464 • Song classification based on MRI.
- 465 • Scan length (minutes).
- 466 • Any discomforts for the child during the scan.

467 **7.2.2 Radiographic results**

468 Injury radiographs and subsequent radiographs during FU will be read and described by a senior
 469 orthopedic surgeon.

470 **7.2.3 Secondary displacement**

471 Any secondary displacement and amount of radiographic displacement (mm) is recorded.

472 **7.2.4 Pain**

473 To quantify pain in the patient, an age appropriate rating scale is applied:

- 474 • Age <5 years: Face, Legs, Activity, Cry, Consolability Scale (FLACC)
- 475 • Age >4 years: Faces Pain Scale – Revised (FPS-R)
- 476 • Age >8 years: Visual analogue scale

477 **Face, Legs, Activity, Cry, Consolability Scale (FLACC)**

479 To quantify pain behaviors in children who may not be able to verbalize the presence or severity of pain
 480 FLACC [38] provides a simple framework. The child is observed for at least 2-5 minutes. Legs and body
 481 are observed uncovered. Activity is observed and body is assessed for tenseness and tone.

482

Behavior	0	1	2
Face	No particular expression or smile	Occasional grimace or frown, withdrawn, disinterested	Frequent to constant quivering chin, clenched jaw
Legs	Normal position or relaxed	Uneasy, restless, tense	Kicking or legs drawn up
Activity	Lying quietly, normal position, moves easily	Squirming, shifting, back and forth, tense	Arched, rigid or jerking
Cry	No cry (awake or asleep)	Moans or whimpers; occasional complaint	Crying steadily, screams, sobs, frequent complaints
Consolability	Content, relaxed	Reassured by touching, hugging or being talked to, distractible	Difficult to console or comfort

483

484 Assessment of Behavioural Score:

- 485 • 0 = Relaxed and comfortable
- 486 • 1-3 = Mild discomfort
- 487 • 4-6 = Moderate pain
- 488 • 7-10 = Severe discomfort/pain

489

[figure not shown]
490

491

492

493 Faces Pain Scale – Revised (FPS-R)

494 The Faces Pain Scale – Revised (FPS-R) [39] is used to quantify pain in children above four years of
 495 age. It is a self-report measure of pain intensity developed for children. It was adapted from the Faces

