- 540 • Continuous variables will be summarized using the mean, standard deviation (SD), median, inter-
541 quartile range, and minimum and maximum values and, if appropriate, according to clinically relevant
542 categories.

543

544 In general, continuous variables with both baseline and FU measurements available will also be
545 summarized in terms of the individual patient-level changes between baseline and follow-up.

546

547 A p-value of <0.05 is regarded as being significant. Data will be analyzed using SPSS (SPSS, Chicago,
548 IL, USA).

549 8.3.1 Patient discontinuation

550

551 If a participant chooses to discontinue the follow-up examinations for any reason, the date and reason
552 for drop-out is recorded and the latest examination will be carried forward in the analysis. In case of
553 drop-out before the first follow-up visit the participant will be excluded from the analysis. Participants are
only removed from the study if they decline participation.

554 9 Bias

555

556 We strive to minimize bias in our study. Minimally displaced fractures of the elbow can go unnoticed and
557 be missed by our project. However, Danish parents are usually not withholding in taking an injured child
558 to the ED. A strict protocol for referrals for treatment are in place in Denmark. All eligible patients
559 referred to Herlev and Gentofte University Hospital will be asked to participate in the study. We
560 speculate that by enrolling 50 participants the cohort will be representative of the background
561 population. We speculate that these efforts will limit selection bias. Efforts described in the follow-up
562 section reduce the risk of loss to follow-up. Overall, we find a low risk of bias in our study for the chosen
study design and size.

563 10 Benefits

564 Classifying lateral condyle fractures and establishing whether they are stable or not is the key to
565 choosing the right treatment strategy. MRI is the only feasible image modality that can make that
566 distinction.

567
568 LHCF is currently a fracture that requires open surgery in most cases due to the radiographic inability to
569 distinguish stable injuries from unstable. This project seeks to use MRI without sedation or GA in order
570 to distinguish fracture patterns. MRI has been shown to be feasible in all age groups without the need
571 for sedation or GA [24].

572
573 Thévenin-Lemoine et.al. found that 25 of 27 children could successfully complete an MRI without

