652 (e.g. late presentation to the ED) that dictate more emergent treatment requiring consent with less
653 consideration time.

654
655 The parents will signify their willingness to let their child participate in the study by signing and dating a
656 personal copy of the approved ICF. The consent form must also be signed and dated by a member of
657 the research team and it will be retained as part of the study records. The investigator will keep the
658 original ICF in the ISF and provide the patient's parents with a copy.

659 **13 Adverse event reporting**

660 In this clinical investigation no medical devices are used and based on the risk analyses, AEs or serious
661 AEs (SAEs) according to ISO 14155 are not collected.

662 **14 Data management**

663 This project complies with the EU's General Data Protection Regulation (GDPR) according to the
664 Danish law on data protection *Databeskyttelsesloven* and *Databeskyttelsesforordningen*.

665
666 In order to plan and conduct visits we ask that consent is given to access the patient's EHR. We ask
667 permission to retrieve patient-related data and to read entries regarding visits. We ask permission to
668 access radiographs and MRIs. We ask that access the patient's EHR is given until the conclusion of the
669 project. No access to the patient's EHR regarding the study is made before informed consent to
670 participate is given.

671
672 Consent gives the person responsible for the trial and the relevant authorities direct access to obtain
673 information in the patient's medical records for the purpose of carrying out the project as well as for
674 control purposes.

675 **14.1 Data collection, source data, storage and archiving**

676 Data management will be performed by the PI. Data handling and protection are conducted according to
677 the ISO 14155 guidelines and ICH-GCP and applicable regulations.

678
679 The eCRF collects data from each participant. Specifically all data on each patient participating in the
680 study are documented in the eCRF. The eCRF contains data items as specified in this CIP. Modification
681 of the eCRF will be made only if deemed necessary and in accordance with any amendment to the CIP.

682
683 The patient's hospital records are stored securely in the hospital's EHR (Epic Systems Corporation,
684 Verona, Wisconsin, USA).

685 **14.1.1 Electronic CRF**

686 For this study, an eCRF is designed to accommodate the specific features of the study design. Access

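### Section 8.3.1 excludes children who drop out before the first follow-up visit from the whole analysis, though the MRI outcomes fall due before Visit 5, and it does not fit sections 6.2.9 and 6.3.5

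*Protocol*

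**What the plan says.** Section 8.3.1 opens with a voluntary act: "If a participant chooses to discontinue the follow-up examinations for any reason, the date and reason" are recorded, and the last examination is carried forward. For earlier leavers it states that in case of "drop-out before the first follow-up visit the participant will be excluded from the analysis". No outcome is exempted. It closes by saying that participants are "only removed from the study if they decline participation".

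The first item in section 7.2.1 is the "Proportion of successful MRIs defined as a completed scan with an image quality that is useful for" analysis by the radiologist. MRI findings, Song stage, scan length and the child's discomfort follow. All of these are obtained at "Visit 4: MRI (5 (± 3) days"). The next scheduled contact for every child is "Visit 5: Radiographs and clinical examination (12 (± 3) days").

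Four other places bear on the rule:

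- **Synopsis:** it lists follow-up from 1 week onward, which falls inside the MRI window.
- **Section 6.2.9:** data already collected from withdrawn patients are to be censored, and in that way taken into account in the analysis.
- **Section 6.3.5:** participation ends if the MRI cannot be completed, if the images are insufficient, or if an unstable fracture is displaced more than 2 mm.
- **Section 14:** families are asked for access to radiographs and MRIs, and access to the "EHR is given until the conclusion of the" project.

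**The concern.** MRI feasibility is the first secondary objective listed in section 5.2, and no follow-up visit is needed to assess it. A rule that removes a child from the analysis for not reaching follow-up can therefore discard a result already in hand, and it shrinks the denominator of the success proportion.

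The children at risk of removal are those who leave around the MRI stage, where failed scans and early operations also occur. MRI success, the Song distribution, initial and final treatment, and secondary displacement could then be reported on a set selected partly by how that stage went. With 50 children, and only a handful of failures or displacements expected, one or two exclusions visibly change a percentage.

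**Working it through.** **Timing.** Visit 4 falls on days 2 to 8 (5 ± 3) and Visit 5 on days 9 to 15 (12 ± 3). The windows do not overlap, so the MRI outcomes precede Visit 5.

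**Which visit is first.** The protocol does not fix this.

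- If it is Visit 5, a scanned child who then leaves loses existing MRI data.
- If it is the 1-week visit in the synopsis, a consented child who leaves before the scan drops out of the feasibility denominator.

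**Sections side by side.** Section 8.3.1 excludes early leavers, while 6.2.9 accounts for data collected from withdrawn patients. Section 8.3.1 removes participants only if they decline, while 6.3.5 ends participation by protocol. No passage says whether a 6.3.5 exit is a drop-out before first follow-up.

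**Inputs.** Planned enrolment is 50 (section 6.1.4). The earlier study cited in section 10 reports 25 of 27 children with a completed MRI and 23 of those 25 treatable non-operatively. Its percentages reproduce: 17/25 = 68%, 6/25 = 24%, 23/25 = 92%. Section 11.3.1 expects secondary displacement close to 4%. The enrolment of 50 has no power calculation to reproduce, and no early drop-out rate is given.

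**Case A: 6.3.5 exits are treated as drop-outs.** At the cited rates:

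- failed scans: 50 × 2/27 = 3.7
- operation suggested on MRI: 50 × 25/27 × 2/25 = 3.7
- remaining: 50 − 3.7 − 3.7 = 42.6

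Every failed or insufficient scan has been removed, so MRI success is 100% by construction, against 25/27 = 92.6%. Initial allocation to non-operative treatment likewise becomes 100%, against 23/27 = 85.2%, because 6.3.5 also suggests operation after a failed scan.

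**Case B: only voluntary leavers are removed.** Assume 46 successes in 50 (50 × 25/27 = 46.3, rounded). If k children leave and j of them are scan failures, the reported success proportion is (46 − (k − j))/(50 − k). The numbers leaving are assumptions.

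| Leavers k | Failures among them j | Reported success |
|---|---|---|
| 0 | 0 | 46/50 = 92.0% (exact 95% CI 80.8–97.8) |
| 1 | 0 | 45/49 = 91.8% |
| 1 | 1 | 46/49 = 93.9% |
| 2 | 0 | 44/48 = 91.7% |
| 2 | 1 | 45/48 = 93.8% |
| 2 | 2 | 46/48 = 95.8% (exact 95% CI 85.7–99.5) |

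**Displacement.** Take 2 events in 50 (4.0%). With two leavers, the reported rate is 2/48 = 4.2%, 1/48 = 2.1% or 0/48 = 0%, according to whether none, one or both of them displaced. The number of events can only stay equal or fall, but the proportion can move either way.

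**The case against.** The strongest reply is that the exclusion sentence directly follows the carry-forward rule, and that section 8.3 speaks of outcomes recorded at scheduled follow-up assessments. On that reading, the analysis means the follow-up analysis: a child with no follow-up examination has nothing to carry forward, and the MRI outcomes are untouched. Section 6.2.9 can be cited in support. This is a reasonable account of what may have been intended, but the sentence carries no such limit, so it should be written in.

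A second reply is that failed scans leave by protocol under 6.3.5, whereas 8.3.1 concerns a participant who chooses to stop. The Case B rows in which failures withdraw voluntarily are then not a typical course of events. This stands, and those rows are illustrations only. It also shows why the status of 6.3.5 exits matters: depending on the answer, 8.3.1 removes none of the failed scans or all of them.

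Three stronger readings are tempting, and the documents do not support them.

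- **Certain favourable bias.** Removing one child with a successful scan lowers the success proportion slightly, to 91.8% from 92.0%.
- **A completers-only analysis from section 3.** That section says "Completely documented means that all FU visits have been carried out for the cases included in the" study, but it describes the cases the site returns and does not define an analysis set.
- **Later outcomes always recoverable from records.** Section 14 asks for access in order to plan and conduct visits. Look-up works only where consent to access persists and usual care recorded the event.

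**Conclusion.** The point holds as a fault of scope and consistency in 8.3.1. Taken literally, the rule can remove MRI outcomes already obtained, or children who never reached the scanner. It contradicts 6.2.9 and leaves the status of 6.3.5 exits undefined.

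The size depends on that status. If those exits count as drop-outs, the feasibility result loses its meaning, because success is 100% whatever happens; the 92.6% comparison assumes that the cited study's rate carries over. If only voluntary leavers are removed, a favourable shift is likely, since a failed or distressing scan is a plausible reason to leave at that stage. It is not certain, and its size cannot be stated without an early drop-out rate. The fault concerns secondary objectives and should be corrected.

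**What to change.** In section 8.3.1:

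- Limit the exclusion to outcomes measured at follow-up visits (MEPS, pain, follow-up radiographs), and name the visit that counts as the first follow-up.
- Analyse MRI feasibility and initial treatment in all consented children for whom an MRI was planned, including those terminated under 6.3.5. Report scans not done separately, by reason, so that logistical reasons are not merged with failed scans. The protocol's enrolled population also requires treatment to have started within the study, so this denominator needs its own definition.
- Report secondary displacement, final treatment and complications on all available data, including records where consent to access persists, and state the number missing for each.

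Then reconcile 8.3.1 with 6.2.9 (what happens to data already collected) and with 6.3.5 (whether termination by protocol is a drop-out). This concerns the analysis only; the clinical content of 6.3.5 is not at issue.

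The cost is a change of wording, slightly more reporting, a record look-up for early leavers where access allows it, and possibly a less favourable success proportion.
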